## **2.2 SUBJECTS**

For the first cohort of participants, up to 50 total study subjects will be recruited from the four FEP clinics in North Carolina (OASIS, Encompass, Eagle, and SHORE), including up to 30 FEP clients and 20 FEP providers (clinicians and PSS). For the second cohort of participants, up to 80 total study subjects will be recruited from the four FEP clinics in North Carolina as well as the UNC-affiliated STEP clinics, including up to 60 FEP clients and 20 FEP providers (clinicians and PSS). All clients who enroll in the study will have a primary diagnosis of a schizophrenia spectrum disorder. Demographic and clinical information that will be

collected as self-report for possible use as covariates includes: 1) demographics: age, sex, ancestry, education, parent education; 2) health: smoking, substance use, current medications, and DUP.

### **2.2.1 INCLUSION CRITERIA**

1. Clients must be between the ages of 16 and 35
2. Clients must have a diagnosis of schizophrenia, schizoaffective disorder, schizophreniform disorder, or Unspecified Schizophrenia Spectrum or Other Psychotic disorder
3. Clients must be receiving services at one of the four FEP clinics in North Carolina (OASIS, Encompass, Eagle, or SHORE) or one of the three UNC STEP-affiliated clinics (Carr Mill Mall, Vilcom Center, Main Wake Clinic)
4. Clients must not have had thoughts of harming themselves in the month before enrollment
5. Clients must not have been hospitalized for psychiatric reasons in the three months before enrollment
6. Clients must not have had a psychiatric medication change in the month before enrollment
7. Clients must have access to the internet through a phone, tablet, or computer

### **2.2.2 EXCLUSION CRITERIA**

1. Clients who do not speak English will not be considered for enrollment
2. Adult clients (18+ years old) with legal guardians (LARs) will not be considered for the study

## **3 ASSESSMENT OF DATA**

At this stage of treatment development, specific outcomes include:

1. Examining the feasibility and acceptability of implementing Horyzons at NC FEP clinics through the following objectives:
  - Assessing change in psychological measures across the three-month (cohort 1) and six-month (cohort 2) study period (primary)
  - Ability to meet our recruitment targets
  - Evaluation of the safety and privacy protocol
  - Evaluating frequency and types of engagement on Horyzons
  - Identifying barriers/facilitators to implementing Horyzons

### **3.1 OUTCOMES**

There are no specific hypotheses associated with this study, as it is an exploratory implementation trial that will test the feasibility and acceptability of Horyzons as a supplementary intervention for individuals in FEP programs.

## **4 STUDY PROCEDURES**

### **4.1 SCREENING/BASELINE PROCEDURES**

#### **4.1.1 SCREENING PROCEDURES**

The research study coordinator will communicate with clinicians and other members of the treatment team to explain the project and discuss eligibility criteria for the study. If agreed to by the clinical team at each site, the research team will review the clinical census at each clinic and/or identify potential participants (clients) via the EPIC system. Clinical team members will be asked to review their current caseloads to identify potentially eligible participants (i.e., patients who are currently receiving services at OASIS, SHORE, Encompass, Eagle, or STEP clinics and are considered clinically stable without current active suicidal ideation). The study coordinator and research assistant will engage in discussion with the treatment team to help identify appropriate clients for inclusion in the project. When participants have been identified and expressed interest in participation to their clinician or other treatment provider, the research study coordinator or RA will reach out to the client in their preferred method of contact (i.e., in person at the clinic or via phone/email) to discuss the project and complete an initial screen to confirm the inclusion and exclusion criteria.

If clients self-refer (in response to flyers), the RA and PI will consult with their treatment team first before screening the client (i.e., to make sure there are no issues that prevent them from safely participating in the study).

Clinicians will be consulted prior to each contact with a prospective participant and asked to advise the research team if any prospective participant should not be contacted.

#### **4.1.2 BASELINE PROCEDURES**

The study coordinator will meet virtually with client participants for approximately 1 hour to complete all baseline measures. Informed consent and HIPAA authorization will be completed first, followed by a demographic form collecting basic information about sex, age, ancestry, education (including parent education levels), cigarette/alcohol use, and basic history of medication/psychosis (including DUP). After completing these documents, the study coordinator will guide participants through virtual copies of the UCLA Loneliness Scale, MOS Social Support Survey, SIAS, and short form PWS. Participants in the second cohort only will complete additional baseline measures (e.g., Questionnaire about the Process of Recovery, Modified Colorado Symptom Index, Social Anxiety Scale for Social Media Users, Twente Engagement Questionnaire). Once all baseline study measures are complete, the study coordinator will guide clients through a 20-30 minute orientation to the Horyzons platform, including creating their personal profile and learning the features of the site. Client participants will be paid \$15.00 via Visa gift card for this hour of their time.

### **4.2 INTERVENTION PERIOD PROCEDURES**

#### **4.2.1 MID-TREATMENT PROCEDURES**

The study coordinator will meet virtually with client participants for approximately 30 minutes to complete the mid-treatment measures. Client participants will complete virtual copies of the UCLA Loneliness Scale, MOS Social Support Survey, SIAS, short form PWS, WAI-I, and Perceived Autonomy Support Scale. Participants in the second cohort only will complete additional measures at mid-treatment (e.g., Questionnaire about the Process of Recovery, Modified Colorado Symptom Index, Social Anxiety Scale for Social Media Users, Twente Engagement Questionnaire). Client participants will be paid \$7.50 via Visa gift card for this 30 minutes of their time.

#### **4.2.2 POST-TREATMENT PROCEDURES**

The study coordinator will meet virtually with client participants for approximately 1-1.5 hours to complete the post-treatment measures. Client participants will complete virtual copies of the UCLA Loneliness Scale, MOS Social Support Survey, SIAS, short form PWS, WAI-I, and Perceived Autonomy Support Scale. Participants in the second cohort only will complete additional measures at post-treatment (e.g., Questionnaire about the Process of Recovery, Modified Colorado Symptom Index, Social Anxiety Scale for Social Media Users, Twente Engagement Questionnaire). After completing these virtual measures, the study coordinator will lead client participants through a feedback survey and individual feedback interview regarding the Horyzons platform, their online therapist, the PSS, and the community newsfeed. Client participants will be welcomed to share their opinions regarding their experience, including suggestions for how to improve Horyzons in the future.

#### **4.2.3 ADDITIONAL ASSESSMENT PROCEDURES**

For participants in the second cohort only, the study coordinator will meet virtually with client participants for approximately .5 hours to complete the measures at 1.5 months following baseline (i.e., between baseline and mid-treatment visits) and 4.5 months following baseline (i.e., between mid-treatment and post-treatment visits). Participants in the second cohort only will complete virtual copies of the WAI-I, Perceived Autonomy Support Scale, and Twente Engagement Questionnaire. Client participants will be paid \$7.50 via Visa gift card for this 30 minutes of their time.

### **4.3 FOCUS GROUPS**

Clinicians and PSS from the four FEP clinics in North Carolina will take part in small focus groups to discuss the feasibility and acceptability of Horyzons as a supplementary intervention at NC FEP clinics. Providers will complete informed consent and a demographic form collecting basic information about their age, sex, race, current position at the clinic, and years of experience in the mental health field over secure Zoom with the study coordinator before being assigned to a focus group. Focus groups will begin with a short feedback survey followed by a group interview led by the

study coordinator. Each group should take approximately 1 hour to complete, and clinician participants will be compensated \$20 via Visa gift card for their time.

## 5 DATA ANALYTIC PLAN

### 5.1 PRIMARY OUTCOME MEASURES

1. Mean Change in UCLA Loneliness Scale Score (Both Cohorts) [Time Frame: up to 6 months]

The UCLA Loneliness scale is a 20 item scale. Answers are on a 4 point scale with options "I often feel this way," "I sometimes feel this way," "I rarely feel this way," and "I never feel this way." Possible scores range from 20 to 80. Higher scores reflect worse outcomes (greater feelings of loneliness). The UCLA Loneliness Scale is a part of the PhenX Toolkit. The UCLA Loneliness Scale is administered in both cohort 1 (Baseline, Mid-treatment, Post-treatment, up to 3 months) and cohort 2 (Baseline, Mid-treatment, Post-treatment, up to 6 months).

2. Mean Change in Medical Outcomes Study (MOS) Social Support Survey – Total Score (Both Cohorts) [Time Frame: up to 6 months]

The MOS Social Support Survey is a 19 item scale. Answers are on a 5 point scale with options "none of the time", "a little of the time", "some of the time", "most of the time", and "all of the time". Possible scores range from 19 to 95. Higher scores reflect higher feelings of social support (more perceived social support). The MOS Social Support Survey is a part of the PhenX Toolkit. The MOS Social Support Survey is administered in both cohort 1 (Baseline, Mid-treatment, Post-treatment, up to 3 months) and cohort 2 (Baseline, Mid-treatment, Post-treatment, up to 6 months).

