**PROTOCOL SYNOPSIS**

|  |   |
|--|---|
| Study Title                               | Horyzons: Implementation in Clinical Practice   |
| Funder                                    | North Carolina Department of Health and Human Services,
University of North Carolina at Chapel Hill  |
| Clinical Phase                            | Phase I   |
| Study Rationale                           | The purpose of the present study is to investigate the feasibility and acceptability of implementing a moderated online social media platform with therapeutic content, Horyzons, as a part of care received at first-episode psychosis (FEP) clinics across North Carolina.  |
| Study Objective(s)                        | 
Examine the feasibility and acceptability of implementing Horyzons at NC FEP clinics through the following objectives:
 
 
1. Assess change in psychological measures across the three-month (cohort 1) and six-month (cohort 2) study period (primary)
 
2. Ability to meet our recruitment targets
 
3. Evaluation of the safety and privacy protocol
 
4. Evaluate frequency and types of engagement on Horyzons
 
5. Identify barriers/facilitators to implementing Horyzons
 
 |
| Test Article(s)
(If Applicable)       | Horyzons is a private digital platform that includes curated therapeutic content surrounding issues such as generalized anxiety, social anxiety, social functioning, depression, and distress tolerance. The site also includes a social media function, in which participants and peer support specialists (PSS) can post text, images, and videos. The site is moderated by graduate students and trained clinicians.   |
| Study Design                              | This is an open trial enrolling both clients from NC FEP clinics. FEP clients will participate in the experimental arm of the trial (access to Horyzons), and FEP clinicians will not. We will also ask clients and clinicians to complete qualitative feedback about Horyzons.   |
| Subject Population                        | Inclusion Criteria   |

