#### **Efficacy Evaluations**

Primary outcomes (both cohorts) - The UCLA Loneliness Scale and MOS Social Support Survey (total score) will be used to assess subjective feelings of loneliness and social support.

Secondary outcomes (both cohorts) - The SIAS and short-form PWS will be used to assess subjective feelings of social anxiety and psychological wellbeing.

Tertiary/Exploratory Outcomes (both cohorts) - Quantitative and qualitative feedback collected at post-treatment and in focus groups will be used to explore feasibility and acceptability of Horyzons as a support tool in NC FEP clinics. Subscales from the MOS Social Support Survey and the short-form PWS as well as total scores from the WAI-I and Perceived Autonomy Support Scale may be explored in data analysis. Among the second cohort only, other scales/subscales such as the Questionnaire about the Process of Recovery, Social Anxiety Scale for Social Media Users, Modified

---

|  |   |
|--|---|
|  | Colorado Symptom Index, and Twente Engagement with eHealth Technologies Scale may be explored in data analysis.   |
| Safety Evaluations              | A safety plan for Horyzons was developed before participants joined the Horyzons digital platform by PI [name] and study coordinator [name]. All safety measures were approved by the director of each NC FEP clinic.   |
| Statistical And Analytic Plan   | Analyses will primarily be descriptive in nature. We will calculate means, standard deviations, and effect sizes of the primary outcomes (loneliness, social support) and secondary outcomes (social anxiety, psychological wellbeing).   |
| DATA AND SAFETY MONITORING PLAN | Privacy and online safety will be managed in accordance with the 'Online social networking' guidelines published by 'Cybersmart', a national cybersafety and cybersecurity education program managed by the Australian Communications and Media Authority (ACMA). Online safety will be monitored by Horyzons moderators (clinicians involved in the project, peer support specialists, graduate students in the Department of Psychology and Neuroscience) with supervision from the Principal Investigator. [name] will function as the Project Medical Officer. |

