For all administration of assessments/interviews, the study coordinator will use screen sharing via secure videoconferencing to complete measures with the participant. Baseline assessment will be completed alongside the review and completion of informed consent and onboarding of participants onto the Horyzons platform. Participants will complete a mid-treatment assessment with the study coordinator or other trained research assistant, which corresponds to approximately 6-8 weeks after onboarding in the first cohort and approximately 12 weeks after onboarding in the second cohort. Participants will also meet with the study coordinator or other trained research assistant for a post-treatment assessment after clients have engaged with the platform for 12 weeks in the first cohort and 26 weeks in the second cohort. At post-treatment, both clients and clinicians (procedures described below) will be provided with an optional feedback form as a way of better understanding their experience with the platform and collecting suggestions for improving the site. Individual feedback interviews with clients will also be completed at post-treatment, lasting 60 minutes. These interviews will address participants' social relationships, experiences with loneliness, and thoughts about connecting with others through Horyzons.

In order to evaluate the extent to which engagement in Horyzons may have impacted participants' perceptions of their social environment, participants will be asked to complete brief psychological measures. In the first cohort at baseline, mid-treatment (6-8 weeks), and post-treatment (12 weeks), participants will complete measures of loneliness (UCLA Loneliness Scale), social support (MOS Social Support Survey), social anxiety (Social Interaction Anxiety Scale), recovery (short form PWS - Psychological Wellbeing Scale), and therapeutic alliance (WAI-I and Perceived Autonomy Support Scale).

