The second cohort will complete all aforementioned measures at baseline, mid-treatment (12 weeks), and post-treatment (26 weeks) alongside additional measures of personal recovery (Questionnaire about the Process of Recovery), social anxiety related to use of social media (Social Anxiety Scale for Social Media Users), and self-report psychological symptomatology (Modified Colorado Symptom Index). A self-report measure of engagement (Twente Engagement with Ehealth Technologies Scale) will be completed at baseline, mid-treatment, and post-treatment as well as at two additional timepoints: 1.5 months and 4.5 months following baseline. Measures of therapeutic alliance (WAI-I and Perceived Autonomy Support Scale) will be administered at 1.5 months, mid-treatment, 4.5 months, and post-treatment only. As this platform will be provided as part of clients' routine clinical care, we will also share clinical impressions and other relevant clinical information to the clinical team at the client's respective FEP clinic.

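### Does Section 5.1 leave the primary mean change undefined because it names no pair of visits?

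*Combined protocol and SAP*

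**What the plan says.** Section 5.1 gives the first primary outcome as "Mean Change in UCLA Loneliness Scale Score (Both Cohorts) [Time Frame: up to 6 months"] and words the MOS Social Support total score the same way. Under each title it lists baseline, mid-treatment and post-treatment administrations, up to 3 months for cohort 1 and up to 6 months for cohort 2. It does not name the two visits whose difference is the mean change.

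The analysis sentence is in the Protocol Synopsis, Statistical and Analytic Plan: "We will calculate means, standard deviations, and effect sizes of the primary outcomes (loneliness, social support"). It names no contrast and no rule for combining cohorts.

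The objective is stated twice by cohort. The Synopsis has "Assess change in psychological measures across the three-month (cohort 1) and six-month (cohort 2) study period (primary"), and Section 3 has "Assessing change in psychological measures across the three-month (cohort 1) and six-month (cohort 2) study period (primary"). The Synopsis entry on study duration says that participation runs from the baseline visit to the post-treatment visit: 3 months in cohort 1, 6 months in cohort 2.

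Section 2.1 fixes the timing. Mid-treatment is "approximately 6-8 weeks after onboarding in the first cohort and approximately 12 weeks after onboarding in the second cohort". Post-treatment comes "after clients have engaged with the platform for 12 weeks in the first cohort and 26 weeks in the second cohort".

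**The concern.** Three visits allow three differences: baseline to mid, baseline to post, and mid to post. If the plan does not say which one is primary, the choice could be made after the data are seen. The label for both cohorts, with a single time frame of up to 6 months, can also be read as one combined figure. Combining by visit label would join week 12 to week 26, or week 6-8 to week 12. Section 5.4 says that the study will inform later randomized pilot trials, so an effect size with no clear follow-up week would be of little use to their designers.

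Week 12 is the only follow-up week at which both cohorts complete the primary scales, so a week-12 change looks like the natural combined estimate. The Synopsis also gives clients three months of access without separating the cohorts, while Section 2.1 gives cohort 2 up to 6 months. That raises the question of what exposure the week-26 change reflects.

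**Working it through.** The plan states no sample size calculation, alpha or assumed SD, so there is no figure of its own to reproduce. The check is in four steps.

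**1. What combining by label would do.** Inputs: 25 and 37 clients (Synopsis), ceilings of 30 and 60 (Section 2.2), and the weeks in Section 2.1. Mean follow-up = (n1·w1 + n2·w2)/(n1 + n2).

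| Combined change | 25 and 37 clients | 30 and 60 clients |
|---|---|---|
| Baseline to post (weeks 12 and 26) | (300 + 962)/62 = 20.4 weeks | (360 + 1560)/90 = 21.3 weeks |
| Baseline to mid (weeks 6-8 and 12) | 9.6 to 10.4 weeks | 10.0 to 10.7 weeks |

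As an illustration, assume that both cohorts have changed by -3 points at week 12. If cohort 2 stands at 0, -3 or -6.5 points at week 26, the combined post change with 25 and 37 clients is -1.2, -3.0 or -5.1. Combining by label would be a poor summary, so the question is whether the plan does it.

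**2. Whether the plan does it.** No section says that cohorts are to be combined. In Section 5.3 the tag for both cohorts alternates with a tag for cohort 2 only, and it is also attached to the qualitative summaries, where no combined number can exist. It marks where a measure is collected. The six-month time frame is the longer of the two, and the text under each title splits it by cohort.

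**3. Which visit pair the plan implies.** The objective gives change over each cohort's study period, and the duration entry gives the ends of that period as baseline and post-treatment. Together they yield week 0 to 12 in cohort 1 and week 0 to 26 in cohort 2. The time frames in Section 5.3 follow the same first-to-last convention. For the alliance and autonomy scales, cohort 1 has up to 6 weeks (12 - 6 = 6, taking mid-treatment at week 6). Cohort 2 has up to 20 weeks (26 - 6 = 20, taking the 1.5-month visit as about week 6).

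**4. What a combined week-12 estimate would add.** The data exist: "The second cohort will complete all aforementioned measures at baseline, mid-treatment (12 weeks), and post-treatment (26 weeks"). Cohort 2's 1.5-month visit offers no other match, because there "Participants in the second cohort only will complete virtual copies of the WAI-I, Perceived Autonomy Support Scale, and Twente Engagement Questionnaire". The 95% half-width in SDs of change is t(0.975, n-1)/√n for one cohort. For the two combined with weights by n it is t(0.975, N-2)/√N. This assumes complete data, equal SDs and independent cohorts.

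| | Cohort 1 | Cohort 2 | Combined |
|---|---|---|---|
| 25 and 37 clients | 0.41 | 0.33 | 0.25 |
| 30 and 60 clients | 0.37 | 0.26 | 0.21 |

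The gain applies to week 12 only; cohort 2's week-26 change keeps its half-width of 0.33. If the true week-12 changes differ by 0.3 SD (an assumption), the combined value lies 0.3 × 37/62 = 0.18 SD from cohort 1 and 0.3 × 25/62 = 0.12 SD from cohort 2. It would join an end-of-treatment visit to a mid-treatment visit. It would also join cohorts enrolled in 2021 and 2022, with the STEP clinics added in the second.

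**The case for a change.** The strongest case for a change is that an objective is not an analysis rule. Section 5 is headed as the analytic plan, so a reader should find the visit pair there and not assemble it from the objectives and the duration entry. One sentence would close the matter at almost no cost, and the later trials do need to know the week behind each effect size.

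The factual part stands: the visit pair is not written in Section 5.1, and the same wording carries into Section 5.2 and the scale outcomes in Section 5.3. What does not follow is that results are at risk. The pieces that fix the contrast are in the same document, agree with one another, and leave no competing reading that the text supports. Such a sentence would be harmless, but it would record what is already implied and alter no estimate. The combined week-12 figure is a preference: nothing in the plan calls for it, and its precision figures do not measure any harm from the missing words.

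The access statements in the Synopsis and Section 2.1 do conflict and must be reconciled. The reading in which cohort 2's last visit falls about 13 weeks after access ended (26 - 13 = 13) sits badly with Section 2.1, which places that visit after 26 weeks of engagement. The conflict is an editorial matter that does not affect which visits are compared.

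**Conclusion.** The concern identifies a gap in wording that analysts will fill sensibly. Read as a whole, the plan gives baseline to post-treatment within each cohort: week 12 in cohort 1 and week 26 in cohort 2. Combining by label would distort the summary (20.4 weeks of average follow-up with 25 and 37 clients), but the plan does not propose it. Section 3.1 states no hypotheses and the Synopsis calls the analysis mainly descriptive, so neither type I error nor power is at stake. A combined week-12 estimate would be more precise (half-width 0.25 SD, against 0.41 and 0.33), but only for a quantity that the plan does not seek and that mixes stages of treatment, clinics and years.

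This conclusion rests on reading the tag for both cohorts as a statement of where the scale is used, and on taking the study period from the Synopsis duration entry. The text supports both readings. No change to the analysis plan is needed.
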